#### Time to protocol-defined event

For patient with an event, it will be defined as the earliest onset time of the following: a protocol-defined relapse, T1 Gd-enhanced lesion, new and/or enlarging T2 lesion, or confirmed disability progression (see below for the determination of the time to onset of confirmed disability progression)

Patients without an event (either during the complete 96-week study period, or before early withdrawal from treatment) will be censored at the last evaluation of a protocol defined event, i.e. the maximum time of last MRI or EDSS evaluation

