6.5.2 Secondary Efficacy Outcome Measures

The secondary efficacy outcome measures are as follows:

- The proportion of patients free from a protocol-defined event during a 24-week period and a 48-week period
- Time to protocol-defined event (see definition above)
- Annualized relapse rate at Week 96
- The time to onset of first relapse
- Time to onset of first T1 Gd-enhanced lesion
- Time to onset of first new and/or enlarging T2 lesion
- Time to onset of CDP for at least 24 weeks during the study period
- Total number of T1 Gd-enhanced lesions detected by brain MRI at Weeks 24, 48, and 96
- Change in total T2 lesion volume detected by brain MRI from baseline to Weeks 24, 48, and 96
- Total number of new and/or enlarging T2 lesions detected by brain MRI at Weeks 24, 48, and 96

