#### 2.2.2 Secondary Efficacy Outcome Measures

- The proportion of patients free from a protocol-defined event during a 24-week period and a 48-week period
- Time to protocol-defined event (as defined in [Section 2.2.1](#) above)
- The time to onset of first relapse
- Time to onset of first T1 Gd-enhanced lesion
- Time to onset of first new and/or enlarging T2 lesion
- Time to onset of confirmed disability progression for at least 24 weeks during the study period
- Annualized relapse rate at week 96
- Total number of T1 Gd-enhanced lesions detected by brain MRI at weeks 24, 48, and 96
- Total number of new and/or enlarging T2 lesions detected by brain MRI at weeks 24, 48, and 96

- Change in total T2 lesion volume detected by brain MRI from baseline to weeks 24, 48, and 96

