#### **4.1.2        Modified Intent-to-Treat Population**

The modified ITT (mITT) population is a subset of the ITT population which excludes patients who discontinued ocrelizumab treatment early without any protocol-defined events for reasons other than death and lack of efficacy.

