##### **4.4.1 Primary Efficacy Endpoint**

The proportion of patients who are free from a protocol-defined event during a 96-week period will be calculated and presented along with a two-sided 95% Clopper-Pearson exact confidence interval. Data from unscheduled visits within each respective 24-week interval will be included in the evaluation of the endpoint. Analyses will be performed for the mITT population. Patients are considered to have a protocol-defined event during the 96-week period if they discontinue due to lack of efficacy or death despite without a protocol-defined event as defined below.

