#### **4.4.2 Secondary Efficacy Endpoints**

The mITT population will be used for secondary efficacy endpoints of the proportion of patients free from a protocol-defined event during the first 24-week and 48-week period.

Analyses of all other secondary efficacy endpoints will be performed using the ITT population.

The proportion of patients free from a protocol-defined event during the first 24-week and 48-week will be presented along with a two-sided 95% Clopper-Pearson exact confidence interval. Same analysis method of the primary efficacy endpoint will be applied to the 24-week and 48-week outcomes. Note that event during the first 24-weeks will not include CDP events due to no confirmatory EDSS score can be observed within the first 24-weeks. A histogram of the percent of patients who are event free at weeks 24, 48, and 96 will be produced.

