### **Time-to-event endpoints**

The Kaplan–Meier method (i.e., the product limit estimator) will be used to estimate the time to onset of the 5 parameters listed below. Kaplan-Meier plots will be produced. The event-free probability at Week 96 will be calculated based on Kaplan-Meier method as sensitivity analyses of the primary endpoint, proportion of patients without a protocol-defined event.

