#### **4.4.4 Sensitivity Analyses**

The analysis of primary efficacy endpoint described in Section 4.4.1 will be performed for the PP population as a sensitivity analysis. Per study schedule, the last EDSS assessment is at Week 96, such that no subsequent visit with EDSS measurement can be used to confirm an initial disability progression at Week 96. A Sensitivity analysis will be performed for the mITT population to impute 50% of the patients with an initial disability progression at Week 96 as having an event of CDP; the other 50% of these patients as having no event of CDP.

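### The Week 96 Kaplan-Meier sensitivity analysis of the primary endpoint censors event-free patients who stop for lack of efficacy or die, although the primary counts them as events

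*SAP*

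**What the plan says.** **Primary analysis.** SAP Section 4.4.1 gives the proportion event-free over 96 weeks in the mITT population and adds a rule for some patients with none of the four components: "Patients are considered to have a protocol-defined event during the 96-week period if they discontinue due to lack of efficacy or death". Section 4.1.2 is built to match. The mITT population "excludes patients who discontinued ocrelizumab treatment early without any protocol-defined events for reasons other than death and lack of efficacy", so event-free patients who stop for those two reasons stay in the denominator as failures.

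**Kaplan-Meier sensitivity analysis.** Section 4.4.2, under Time-to-event endpoints, states: "The event-free probability at Week 96 will be calculated based on Kaplan-Meier method as sensitivity analyses of the primary endpoint". The population follows from the start of that section: "Analyses of all other secondary efficacy endpoints will be performed using the ITT population". Under Time to protocol-defined event, the event is the earliest of a relapse, a T1 Gd-enhanced lesion, a new or enlarging T2 lesion, or confirmed progression. Everyone else is handled by one rule: "Patients without an event (either during the complete 96-week study period, or before early withdrawal from treatment) will be censored at the last evaluation", meaning the later of the last MRI and the last EDSS.

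**Other sensitivity analyses.** Section 4.4.4 has two. One is on the per-protocol population: "The analysis of primary efficacy endpoint described in Section 4.4.1 will be performed for the PP population as a sensitivity analysis". The other is on mITT and imputes half of the unconfirmed Week 96 progressions as events.

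**The concern.** A patient who gives up treatment for lack of efficacy, or who dies, before any of the four components is recorded is a failure in the primary. In the analysis meant to test the primary, that patient leaves the risk set as though the later course would resemble that of patients who stayed. For a stop due to lack of efficacy, that assumption is doubtful, and the censoring is plausibly informative.

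The Kaplan-Meier estimate therefore differs from the primary in two ways. It brings back, through censoring, the event-free patients who stopped for other reasons and whom mITT excludes. It also drops the Section 4.4.1 rule. The first difference is a reasonable thing to vary. The second moves the estimate in the favourable direction only, and the single reported number does not show how much of any difference comes from which source. It is the only planned sensitivity analysis of the primary on the full ITT population, and the only one that drops the rule.

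**Working it through.** **Step 1: the yardstick.** Protocol Section 6.1 assumes 45% event-free and a 95% CI half-width of 4 points. With a Wald interval, n = 1.96² × 0.45 × 0.55 / 0.04² = 594.2. Requiring an 80% probability that the half-width is at most 4 points gives n = 598 by exact binomial calculation. The protocol states 598.86, rounded to 600, so its figure reproduces. At n = 600 the half-width is 1.96 × √(0.45 × 0.55 / 600) = 3.98 points.

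**Step 2: does the Section 4.4.1 rule carry over?** Its sentence concerns the primary proportion. The time-to-event text has its own closed event list and gives no event time for a lack-of-efficacy stop or a death. SAP Section 2.2.2 defines the endpoint by reference to Section 2.2.1, which lists only the four components. A programmer following the text would censor these patients.

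**Step 3: direction and formula.** Let a share q of all patients stop event-free at time t for lack of efficacy or death, with no other dropout.
- Censored, as written: KM(96) = S(96).
- Counted as events: KM(96) = (S(t) − q) × S(96)/S(t).
- Gap = q × S(96)/S(t). It is never negative and never exceeds q.

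**Step 4: size.** S(96) = 0.45 is from the protocol. The path to it and q are assumptions. Stops are spread evenly after Weeks 24, 48 and 72.

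| Assumed curve | S(96)/S(t) at Weeks 24, 48, 72 | Mean | Gap, q = 1% (6 of 600) | Gap, q = 2% (12 of 600) |
|---|---|---|---|---|
| Constant hazard | 0.45^0.75 = 0.549; 0.45^0.5 = 0.671; 0.45^0.25 = 0.819 | 0.680 | 0.68 points | 1.36 points |
| Early events: S = 0.65, 0.55, 0.50 | 0.45/0.65 = 0.692; 0.45/0.55 = 0.818; 0.45/0.50 = 0.900 | 0.803 | 0.80 points | 1.61 points |

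With q = 0 the gap is zero.

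**Step 5: what the documents suggest about q.** They give no count of lack-of-efficacy stops. Deaths alone should add little. Protocol Section 1.2.1.2 reports 1 death in the pooled ocrelizumab arms of the two RMS trials. In the same arms 4 patients are 0.5%, so the arms held about 4/0.005 = 800. That is about 0.75 deaths per 600, q = 0.125%, and a gap of about 0.1 point (0.125 × 0.680 to 0.803). Footnote c of Protocol Appendix 1 requires the assessments at discontinuation, apart from an MRI done in the previous 8 weeks. That should limit how many lack-of-efficacy stops remain event-free.

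**Step 6: the two differences mixed.** Take the constant-hazard curve, 600 patients, 6 event-free stops for lack of efficacy or death, and 30 event-free stops for other reasons (both counts assumed).
- Kaplan-Meier as written: 45.0%.
- Kaplan-Meier with the Section 4.4.1 rule: 44.3%.
- mITT primary, 570 patients: 43.1%.

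Of the 1.9-point difference from the primary, 0.7 comes from dropping the rule and 1.2 from the other stoppers. Only the 1.9 would be visible. With no other stoppers, the Kaplan-Meier estimate with the rule equals the primary exactly (44.3% in both).

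**The case against.** The best defence is that the protocol-defined event has four components wherever it is defined. Protocol Section 6.7 left event-free early stoppers to the SAP as a missing-data matter. The Section 4.4.1 sentence and the mITT exclusion are then one handling rule, and Kaplan-Meier replaces both with another: censor every event-free early stopper. Varying missing-data handling is a normal job for a sensitivity analysis. The discontinuation reasons tabulated under SAP Section 4.2 also let a reader cap q, and so bound the effect.

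Much of this stands. Censoring is a legitimate alternative for patients who leave for other reasons, the four-component secondary endpoint is sound, and the effect can be bounded and may be nil. Two things do not follow. Censoring at a stop for lack of efficacy is plausibly informative, so it is a weak test of a primary that calls such patients failures. And a count of reasons bounds the shift without correcting the estimate.

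A reader might go further and infer that Kaplan-Meier is the only analysis that retains the early stoppers mITT drops. The documents do not support that. SAP Section 4.1.3 draws the per-protocol population from ITT, and Appendix 5 lists only eligibility violations as reasons for exclusion. The per-protocol analysis may therefore retain event-free stoppers too, with the Section 4.4.1 method applied. Nor does the SAP say that the Kaplan-Meier estimate exists to show the effect of the mITT exclusion.

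**Conclusion.** The inconsistency is real on the text. The Week 96 Kaplan-Meier estimate is labelled a sensitivity analysis of the primary, yet it censors event-free lack-of-efficacy stops and deaths that the primary counts as events. The effect is upward or nil. It is zero with no such patients, roughly 0.7 to 0.8 points at an assumed 1% and 1.4 to 1.6 points at an assumed 2%. These figures rest on the protocol's 45%, two assumed curves, evenly spread stops and no other dropout. At these rates the shift is well inside the planned 4-point half-width.

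A reader might infer that the primary result is biased. It is not: the primary estimate and its confidence interval do not use this rule. This is a cheap improvement worth considering, not a threat to the trial's conclusion.

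**What to change.** In SAP Section 4.4.2, Time-to-event endpoints, after the sentence naming the Week 96 sensitivity estimate, add: *For this estimate only, discontinuation for lack of efficacy, or death, without a prior protocol-defined event counts as an event at the discontinuation or death time, as in Section 4.4.1.* Leave the four-component secondary endpoint and its censoring rule unchanged, and label the two Kaplan-Meier results so that each shows its event definition.

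The cost is one sentence and one derived event flag. No new data are needed, because reasons for stopping are already collected and tabulated. The drawback is that two Kaplan-Meier event definitions sit side by side. A difference from the mITT primary will remain, but it will then reflect only how the other early stoppers are handled.

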#### Time to onset of first relapse

For patients with an event, it will be determined as the first relapse time reported by the patient.

Patients without any relapse will be censored at the last study visit.

#### Time to onset of first T1 Gd-enhanced lesion

For patient with event, it will be defined as the first time a T1 Gd-enhanced lesion was detected post baseline.

Patients without an event will be censored at the last performed MRI evaluation.

#### Time to onset of first new and/or enlarging T2 lesion

For patient with event, it will be defined as the first time, including at unscheduled visits, a new and/or an enlarging T2 lesion was detected.

Patients without an event will be censored at the last performed MRI evaluation.

Time to onset of confirmed disability progression determination for at least 24 weeks during the study period

For patient with an event, it will be defined as the initial disability progression time.

Patients without an event will be censored at the last available EDSS evaluation.

The adjusted annualized relapse rate at Week 96 will be estimated using a negative binomial model, adjusting for the number of previous DMTs (1 or  $>1$ ), baseline EDSS ( $< 2.5$  vs  $\geq 2.5$ ), and including the log-transformed years of drug exposure time as an “offset” variable. The adjusted rates along with the two-sided 95% confidence interval will be presented. SAS proc GENMOD will be applied. Years of drug exposure will be defined as ((earlier of date of Week 96 visit or date of treatment early termination) – date of first infusion + 1)/365.25

The unadjusted annualized relapse rate at Week 96 will be presented. It is defined as the total number of relapses for all patients divided by the total years of drug exposure.

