6.5.4 Analysis Methods

The proportion of patients who are free from a protocol-defined event during Week 96 (the primary efficacy endpoint) will be calculated, and the two-sided 95% CI will be presented. Data from any unscheduled visit within each respective 24-week interval will be included for this endpoint. Similar analyses will be applied to the proportions of patients who are free from a protocol-defined event during Weeks 24 and 48.

The annualized relapse rates by Week 96 will be analyzed using negative binomial model, adjusting for the number of previous DMTs used and including the log-transformed year of drug exposure time as an “offset” variable. The adjusted annualized relapse rate and the two-sided 95% CI for the relapse rate will be presented.

The Kaplan-Meier estimator (i.e., the product limit estimator) will be used to estimate the survival function for time-to-event data (e.g., time to protocol-defined event; time to onset

of first relapse; time to onset of CDP for at least 24 weeks). The proportion of patients with an event and of those censored will be reported; the median survival time and its 95% CI will be presented.

The total number of T1 Gd-enhanced lesions will be calculated as the sum of the individual number of T1 Gd-enhanced lesions at Weeks 24, 48, and 96. Data from other unscheduled assessments will not be included in this summary or analysis. A negative binomial model will be used to estimate the rate of lesion occurrence. In order to account for patients receiving varying numbers of brain MRI scans during the study, the log-transformed number of brain MRI scans received will be included in the model as an “offset” variable for appropriate computation.

The change from baseline in total T2 lesion volume as detected by brain MRI to Weeks 24, 48, and 96 will be analyzed through a mixed model with repeated measure (MMRM), adjusting the following covariates: baseline score and the number of previous DMT use.

The total number of new and/or enlarging T2 lesions will be calculated as the sum of the individual number of new and/or enlarging T2 lesions at Weeks 24, 48, and 96. Data from unscheduled assessments will not be included in this summary or analysis. The analysis model will be similar to that used for the total number of T1 Gd-enhanced lesions.

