Appendix 1 **Schedule of Activities (cont.)**

- ^p Neurological examinations will be used to distinguish relapse in MS from another neurological (non-MS) disorder. Potential relapses should be recorded throughout the treatment period. Investigators will also screen patients for signs and symptoms of worsening neurological function localized to the cerebral cortex, such as cortical symptoms/signs, behavioral and neuropsychological alteration, retrochiasmal visual defects, hemiparesis, cerebellar symptoms/signs (e.g., gait abnormalities, limb incoordination). Patients with suspected PML should be withheld from ocrelizumab treatment until PML is ruled out by complete clinical evaluation and appropriate diagnostic testing (see Appendix 6). A patient with confirmed PML should be withdrawn from the study.
- ^q PRO assessments will consist of the following: Multiple Sclerosis Impact Scale 29 (MSIS-29), the Treatment Satisfaction Questionnaire for Medication (TSQM II), and the Treatment Satisfaction with Medicines Questionnaire (SATMED-Q). PROs completed at baseline should be in reference to the last-used DMT prior to enrollment. Please note that all PROs are required to be administered prior to administration of study drug and prior to any other study assessment(s) to ensure the validity of the instruments is not compromised.
- ^r Should only be done at scheduled visits unless PML is suspected.
- ^s MRI has to be conducted before the baseline visit, and results must be available prior to treatment. Prior to initiation of treatment on Day 1/Baseline, a QC report for the baseline MRI scan must have been received from the centralized reading center confirming scan passed QC. The brain MRI requires approximately 2 business days to be quality checked before dosing of ocrelizumab.

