## **Appendix 4** **Programming Codes for Statistical Analyses**

Kaplan-Meier method

```
proc lifetest data=dataset method=km conftype=loglog outsurv=surv  
plots=none notable STDERR;  
    time aval*eventyn(1);  
run;
```

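### MRI lesions are dated at the detecting scan and analysed by ordinary Kaplan-Meier, so the time-to-event curves and medians largely follow the scan schedule, and the Week 96 Kaplan-Meier check is safe only with nominal scan dates

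*SAP*

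**What the plan says.** SAP 4.4.2 (Time-to-event endpoints) states that the Kaplan-Meier method "will be used to estimate the time to onset of the 5 parameters listed below". Three of the five use MRI findings:

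- First T2 lesion: "it will be defined as the first time, including at unscheduled visits, a new and/or an enlarging T2 lesion was detected".
- First T1 Gd-enhanced lesion: "it will be defined as the first time a T1 Gd-enhanced lesion was detected post baseline".
- Time to protocol-defined event: "it will be defined as the earliest onset time of the following: a protocol-defined relapse, T1 Gd-enhanced lesion, new and/or enlarging T2 lesion", with confirmed disability progression as the fourth component.

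The SAS statement in SAP Appendix 4 opens with "time aval*eventyn(1". It has one time variable and one censoring flag, with no place for interval bounds. Protocol 6.5.4 adds that "the median survival time and its 95% CI will be presented". SAP 4.4.2 adds plots and uses the Kaplan-Meier event-free probability at Week 96 as a sensitivity analysis of the primary endpoint.

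The scan times follow from Protocol 6.5.2 ("Total number of new and/or enlarging T2 lesions detected by brain MRI at Weeks 24, 48, and 96") and Protocol Appendix 1, which shows no MRI at Week 72. On other scans, an Appendix 1 footnote says: "Should only be done at scheduled visits unless PML is suspected". SAP 4.4 drops scans done for suspected PML from the efficacy analyses. The only other source is the early-withdrawal MRI, which may be skipped if one was done within the previous 8 weeks.

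**The concern.** These endpoints are named as times to onset, but for lesions the recorded time is the date of the first positive scan. A lesion first seen at Week 96 after a clean Week 48 scan arose at some point in a 48-week gap. Kaplan-Meier treats the scan date as the exact event time, so the curve stays too high between scans and drops at the scan. Neither document mentions interval censoring, midpoint dating or a sensitivity analysis for detection date.

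In a randomised comparison with a shared schedule, part of this delay would cancel. This study has one arm, so the absolute times and curves are themselves the result.

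A second issue concerns the Week 96 probability. The Week 96 visit is Day 673 ± 14 days. SAP 4.4 leaves visit windows to a separate Module 2 and does not say whether scans are dated by actual day or nominal week. With actual dates, patients scanned clean leave the risk set while others still await the same scan, and Kaplan-Meier then misreads the whole window.

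**Working it through.** **The plan's own figure.** The documents give no figure for these endpoints. The related figure is the sample size in Protocol 6.1: 598.86, rounded to 600. The smallest n for which the Wald 95% half-width is at most 0.04 with probability at least 0.80 at p = 0.45 is 598 by exact binomial (probability 0.826; 0.741 at n = 597). It reproduces.

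**Inputs.** From the documents: 45% composite event-free at Week 96 (Protocol 6.1); scans at Weeks 24, 48 and 96; window ±14 days. Assumed: constant hazard; MRI share m of the first-event hazard from 25% to 100%; the remaining events dated exactly; no dropout; scan dates uniform over the window where actual dates are used.

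**True values.** λ = −ln(0.45)/96 = 0.00832 per week. Median = ln 2/λ = 83.3 weeks. Event-free at Week 48 = 0.45^(48/96) = 67.1%; at Week 72 = 0.45^(72/96) = 54.9%.

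**Delay if every event is a lesion (m = 1).** The mean gap from onset to detection is 12.4 weeks for the 24-week intervals and 25.6 weeks for the 48-week interval; overall 17.7.

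**Week 72 in the composite.** Between Weeks 48 and 96 only the exactly dated events move the curve, so it reads 0.45^([48m + 72(1 − m)]/96).

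| MRI share m | Kaplan-Meier at Week 72 | True |
|---|---|---|
| 100% | 67.1% | 54.9% |
| 75% | 63.8% | 54.9% |
| 50% | 60.7% | 54.9% |
| 25% | 57.8% | 54.9% |

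**Composite median.** With nominal dates the curve crosses 50% before Week 96 only if t = (83.3 − 48m)/(1 − m) is below 96. At m = 25%, t = (83.3 − 12)/0.75 = 95.1. At m = 50%, t = 118.7, so the crossing comes at the Week 96 drop. The changeover is at m = (96 − 83.3)/48, about 26%. Simulation with n = 600 gives a mid-run median of about 96 weeks for m of 50% or more. At m = 25% it gives 94 to 95 weeks, with a mean over runs of 92 to 93. Adding an assumed 8% dropout, with actual dates, lowers that mean to 90.9.

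**Week 96 probability with actual dates, m = 1.** Of patients lesion-free at Week 48, a fraction f = (0.671 − 0.45)/0.671 = 0.329 will be positive at the last scan. As patients are scanned, S(t) = 0.671 × r^f, where r is the fraction not yet scanned. At Week 96, r = 0.5 and S = 0.671 × 0.5^0.329 = 0.534, or 0.530 on whole-day dates. On the last of the window's 29 days, S = 0.671 × the product over k = 1 to 29 of (1 − 0.329/k) = 0.16. With nominal dates it reads 0.45, which is correct.

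**T2 alone.** The documents give no T2-only rate. Under the planned 55% with any event, a T2 median is reached with nominal dates only if about 50/55 = 91% of those patients have a T2 lesion. At 55% T2-free (true median 111.3 weeks) the nominal-date median is not reached in 99% of runs. With actual dates the same formula gives f = 0.258 and a crossing at r = (0.5/0.742)^(1/0.258) = 0.217, so a median of 98 − 4 × 0.217 = 97.1 weeks. At 65% T2-free (true median 154.5 weeks) it gives 97.7 weeks.

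**The case against.** The SAP says openly that lesions are dated when detected, and dating events at the detecting visit is common practice. The study is mostly descriptive, these are three of ten secondary efficacy measures, and composite event-free proportions at Weeks 24, 48 and 96 with exact intervals are already planned. Relapses are dated at reported onset, so the composite is only partly tied to the scans. All of this is fair, and it limits the weight of the point. It does not make the promised median or the plotted curve correct.

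Three stronger readings are tempting, and the documents do not support them.

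- A reader might infer that the T2 median will be 96 weeks whatever the disease does, by applying the 45%, or the 32% benchmark, to T2 lesions alone. The 45% is a composite figure, and the 32% is a composite no-disease-activity figure for another drug. The T2 median may simply not be reached.
- A reader might infer that the Kaplan-Meier estimate at Week 96 is safe in any case, or that it is certainly wrong. It depends on nominal or actual dating, which the SAP defers to Module 2.
- A reader might infer that the primary result is biased. The primary endpoint is a simple proportion over 96 weeks and does not use the dates in this way.

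**Conclusion.** The concern holds for the three MRI-based time-to-event endpoints. Under a constant hazard, 45% event-free and no dropout, the composite median typically comes out about 11 to 13 weeks late (94 to 96 against 83). Week 72 is overstated by about 3 to 12 percentage points as the MRI share goes from 25% to 100%. The share and the hazard shape are assumptions, since the documents give no component split. For T2 alone, no size can be given for the median.

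The Week 96 Kaplan-Meier probability is correct with nominal scan weeks. With actual dates uniform over the window and all events MRI-detected, it reads about 0.53 instead of 0.45 and falls to about 0.16 by the end of the window. A spurious median near Week 97 to 98 then appears even when 55% to 65% stay lesion-free. This matters because the figure is meant to check the primary result.

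**What to change.** - **First T2 lesion and protocol-defined event:** replace Kaplan-Meier with an interval-censored (Turnbull) estimator, for example PROC ICLIFETEST. Bound each lesion by the last negative scan and the first positive scan.
- **Composite bounds:** the lower bound is the last assessment at which all components were known to be negative; the upper bound is the earliest observed event. Treat a relapse as exact only if the next scan shows no new lesion; otherwise use the interval from the last negative scan to the relapse date. Bound disability progression below by the preceding EDSS visit.
- **Reporting:** tabulate event-free probabilities at Weeks 24, 48 and 96, and give the median only as an interval. In the lesion-only example above it would be reported as lying between Weeks 48 and 96.
- **Where Kaplan-Meier is kept,** including the Week 96 sensitivity analysis of the primary endpoint: state that scan dates are set to the nominal week.
- **T1 Gd-enhanced lesions:** these are visible only while enhancing, so relabel the endpoint as time to first detection and report cumulative proportions at the three scans.

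The cost is SAP wording and one extra SAS procedure; no new data are needed. The downside is that a median may be a range or not estimable.
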